4.3.2 Handling missing data

Missing safety data will not be imputed.

Missing pharmacodynamics biomarker data will not be imputed since no missing data are expected for the primary pharmacodynamics biomarker variables. Patients are required to have evaluable paired tumour samples for the primary endpoint by central pathology assessment, patients who don't meet this criterion will be replaced.

In general, other than for the below described, or where otherwise specified in the particular analysis, missing data will not be imputed and will be treated as missing.

4.3.2.1 Imputation of Adverse Event and Concomitant Medication Start Date

Missing day: impute with the 1st of the month unless month and year are same as month and year of first dose of study drug then impute first dose date.

Missing day and month: impute with 1st January unless year is the same as first dose date then impute first dose date.

Completely missing: impute with date of first dose of study treatment, unless the end date suggests it could have started prior to this in which case impute with 1st January of the same year as the end date.

When imputing a start date ensure that the new imputed date is sensible i.e. is prior to the end date of the AE or medication.

4.3.2.2 Imputation of Adverse Event and Concomitant Medication End Date

Missing day: impute with the last day of the month, unless month and year are the same as month and year of last dose of study treatment, then impute with the last treatment date in that month.

Missing day and month: impute with 31st of December unless the year is the same as the year of last dose of the study treatment, then impute with the last treatment date of that year.

Completely missing: assume the event is still ongoing and do not impute any date.

Generally, the imputation of dates is to decide if an observation is treatment emergent for AEs or concomitant for medications. Flags will be retained in the database indicating where any

programmatic imputation has been applied, and in such cases, durations and study days will not be calculated.

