4.11.2 Adverse Events

AEs and SAEs will be collected throughout the study from date of informed consent until the end of the safety follow-up period (28 days after last dose of study treatment). The latest version of MedDRA will be used to code the AEs. AEs will be graded according to the National Cancer Institute of Common Terminology Criteria for AEs (CTCAE) version 5.0.

Events will be defined as treatment-emergent AEs, and reported in the summary tables if they onset or worsen (by investigator report of a change in CTCAE grade), during the treatment period as defined in the CSP or during the 28-day safety follow-up period. Any events in this period that occur after a patient has received further therapy for cancer (following discontinuation of study treatment) will be flagged in the data listings.

During the evaluation of the AE data prior to database lock, an AZ medically qualified expert will review the list of AEs that were not reported as SAEs and AEs leading to discontinuation of study treatment. Based on the expert's judgment, significant AEs of particular clinical importance may, after consultation with the Global Patient Safety Physician, be considered other significant AEs (OAEs) and reported as such in the CSR. A similar review of laboratory/vital signs/ECG data will be performed for identification of OAEs.

Examples of these could be marked haematological and other laboratory abnormalities, and certain events that lead to intervention (other than those already classified as serious), dose reduction or significant additional treatment.

Some clinical concepts (including some selected individual preferred terms and higher-level terms) are considered to be "AEs of special interest" (AESIs). AESIs represent pre-specified risks that are considered to be of importance to a clinical development program. These AESIs, if applicable, will be identified as a list of categories provided by the patient safety team.

Reviews will take place prior to database lock to determine whether any AE should be classified as AESIs. The review will identify which higher-level terms, and which preferred terms should contribute to each AESI.

In general, all AE summary tables include only TEAEs. AEs occurring prior to dosing or starting more than 28 days after discontinuation of study drug will be flagged in listings and will not be included in any summaries.

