All reported AEs will be listed along with the actual treatment received at the time of onset, date of onset, date of resolution (if AE is resolved), investigator's assessment of CTCAE grade, relationship to study treatment, action taken and outcome. Frequencies and percentages of patients reporting each preferred term will be presented (i.e., multiple events per patient will not be accounted for, except for event level summaries).

Summaries of adverse events (the number and percentage of patients by treatment) by MedDRA System Organ Class (SOC) and Preferred Term (PT) will include but are not limited to:

- All AEs
- All AEs possibly related to study treatment
- AEs of CTCAE grade 3 or higher
- AEs of CTCAE grade 3 or higher, possibly related to treatment
- AEs with outcome of death
- All SAEs
- All SAEs possibly related to study treatment
- AEs leading to discontinuation of treatment

- AEs leading to discontinuation of treatment, possibly related to treatment
- SAEs leading to discontinuation of treatment
- SAEs leading to discontinuation of treatment, possibly related to treatment
- Other significant AEs (if applicable)
- AESIs (if applicable)

An overall summary of the number and percentage of patients in each of the above categories will be presented, as well as an overall summary of number of events in each of the above categories. In addition, a truncated AE table of most common AEs, showing all events that occur in at least 5% of patients overall will be summarised by PT, by decreasing frequency.

Additionally, an event level summary will be presented for all AEs by PT.

Summaries of the number and percentage of patients with AEs will also be produced by maximum reported CTCAE grades, SOC and PT.

All AESI PTs, if applicable, searched for in this study will be presented. Summaries of AESIs will be presented by maximum reported CTCAE grade, by AE outcome, including time of resolution (on-treatment, follow-up or post-treatment), whether treatment was received (yes/no) and action taken.

In addition, AEs with outcome death, SAEs, AEs leading to discontinuation of treatment and OAEs will be listed separately.

Covid-19 AEs will also be collected and reported by MedDRA System Organ Class.

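### Partial AE and medication end dates are set to the last dose date, so follow-up events can be given an end before their known onset and AESI resolution periods can be misplaced

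*SAP*

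**What the plan says.** SAP section 4.3.2.2 has three rules for AE and concomitant medication end dates.

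- Day missing: use the last day of the month, but if the month and year are those of the last dose, "then impute with the last treatment date in that month".
- Day and month missing: use 31 December, but if the year is that of the last dose, "then impute with the last treatment date of that year".
- Completely missing: treat as ongoing and impute nothing.

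The section adds that imputation generally serves to settle treatment-emergent status for AEs and concomitant status for medications. Imputed dates are flagged, and no duration or study day is computed from them.

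The only plausibility check is in section 4.3.2.1: "When imputing a start date ensure that the new imputed date is sensible i.e. is prior to the end date of the AE or medication". Section 4.3.2.2 has no counterpart for imputed end dates.

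Section 4.11.2 collects AEs "until the end of the safety follow-up period (28 days after last dose of study treatment" and counts an AE as treatment-emergent if it starts or worsens "during the treatment period as defined in the CSP or during the 28-day safety follow-up period". The same section plans to summarise AESIs, if applicable, "by AE outcome, including time of resolution (on-treatment, follow-up or post-treatment").

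**The concern.** The last-dose exception assumes that an event ending in the month of the last dose ended no later than that dose. This design makes the assumption a poor one. Dosing lasts 5 to 7 days in Stages 1 and 2 and 12 to 15 days in Stage 3, followed by 28 days of AE collection, so most of the AE window from first dose lies after the last dose.

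Two errors follow.

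- An event that starts in follow-up, and whose end is known only to the month or year, can be given an end date before its own recorded onset.
- An event that starts on treatment and resolves in follow-up can be recorded as having resolved by the last dose.

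The first is an impossible date in the AE data. The second is a plausible-looking date that always errs towards earlier resolution, and one planned summary sorts AESIs by period of resolution. A medication started after the last dose can likewise be given a stop date before its start.

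**Working it through.** The SAP gives no figure of its own on this point, so there is none to reproduce. The check applies the section 4.3.2.2 rule literally.

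**Example 1, follow-up onset.** Last dose 7 June, AE onset 20 June, end recorded as June. The month matches the last dose, so the imputed end is 7 June, which is 20 − 7 = 13 days before onset. The ordinary month-end rule would give 30 June.

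**Example 2, on-treatment onset.** Last dose 7 June, onset 5 June, true end 15 June, recorded as June. The imputed end is again 7 June. The order of dates is valid, but the resolution has moved from follow-up to on-treatment.

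**Share of the window after the last dose**, 28/(28 + days dosed):

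- Stages 1 and 2: 28/33 = 85% (5 days) and 28/35 = 80% (7 days).
- Stage 3: 28/40 = 70% (12 days) and 28/43 = 65% (15 days).

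**How often the end precedes the start, follow-up onset.** Assumptions: last dose equally likely on each day of a 365-day year (2022 calendar: seven 31-day months, four 30-day months, one 28-day month); onset equally likely on days 1 to 28 after the last dose; AE length A days; end date recorded even if it falls after day 28. For a last dose on day d of a month of L days, the end falls in the same month for min(28, max(0, L − d − A + 1)) of the 28 onset days. S(L) is the sum over d. The share is [7·S(31) + 4·S(30) + S(28)] / (365 × 28 = 10,220).

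| A (days) | S(31) | S(30) | S(28) | Total | Share |
|---|---|---|---|---|---|
| 1 | 462 | 434 | 378 | 5,348 | 52% |
| 4 | 378 | 351 | 300 | 4,350 | 43% |
| 8 | 276 | 253 | 210 | 3,154 | 31% |
| 15 | 136 | 120 | 91 | 1,523 | 15% |

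Longer AEs are affected less because more of them end in a later month, where the ordinary month-end rule applies.

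With day and month both missing, the same formula with L = 365 gives 9,814/10,220 = 96% for A = 1 and 9,422/10,220 = 92% for A = 15.

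**How often resolution is wrongly placed on treatment, end day missing.** Take AEs that start on a dosing day (each equally likely) and truly end j days after the last dose. The end shares the last-dose month unless the last dose falls in the final j days of one of the 12 months, so the share is 1 − 12·(mean j)/365.

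| Days dosed | 8-day AE: mean j | Share | 15-day AE: mean j | Share |
|---|---|---|---|---|
| 5 | 5 | 84% | 12 | 61% |
| 7 | 4 | 87% | 11 | 64% |
| 12 | 4 | 87% | 8.5 | 72% |
| 15 | 4 | 87% | 7.5 | 75% |

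**Does the exception serve the stated purpose?** Treatment-emergent status rests on onset or worsening (section 4.11.2), so the end date does not enter. Concomitant status needs a stop date on or after first dose (section 4.8). Wherever the exception applies, the last dose, month-end and 31 December all fall on or after first dose, so the classification is the same with or without it. The exception helps neither decision.

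**The case against.** The strongest defence is that almost nothing reported depends on these dates. Section 4.3.2.2 says what imputation is generally for, and the end-date rule gives the right answer for that purpose. Incidence, grade, serious AE, discontinuation and death tables do not use the end date. A reader might infer that negative durations will be reported; they will not, because durations and study days are withheld for imputed dates. AESIs are presented only if applicable, and the SAP does not state that imputed end dates feed the time-of-resolution summary.

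All of this stands, and it limits the point to inverted dates in the AE and medication data and one conditional table. It does not remove the point. A period of resolution is neither a duration nor a study day, so the safeguard does not cover it, and it is the only AE summary described that needs an end date. That the table will use imputed dates is therefore an inference from the text, though a close one.

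A reader might also infer that the start-date rule removes treatment-emergent events. For a completely missing start date, section 4.3.2.1 uses first dose "unless the end date suggests it could have started prior to this in which case impute with 1st January" of the year of the end date. Read literally, the exception could cover any event that ended after first dose, and pre-dose events are left out of the AE summaries. That reading would leave the section's own default almost never applicable, so it is unlikely to be meant. The wording needs clarifying; it does not show that events are lost.

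**Conclusion.** The end-date rule is wrong as written for this design. It can give an end date before a known onset, no stated check prevents that, and the exception contributes nothing to either classification that imputation is meant to support.

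The percentages are shares of AEs with a partial end date in the last-dose month or year situations described, not of all AEs. They rest on the assumed AE lengths and evenly spread dates. The 52% and 96% figures are for 1-day AEs and are the upper ends of their ranges. The number of partial dates is not given, so the number of affected events cannot be stated and may be small.

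A reader might conclude that the rule makes the drug look safer across the AE tables. The documents do not support that: AE incidence, treatment-emergent status, concomitant status and durations do not change, and the pharmacodynamic analyses are untouched. The one-way shift towards earlier resolution is confined to the AESI time-of-resolution summary, if that is produced from imputed dates. The correction is worth making before database lock because it is cheap and the defect is certain, not because the effect on conclusions is large.

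**What to change.** In section 4.3.2.2:

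- Delete the last-dose exception from both partial-date rules.
- Impute the earliest of the last day of the known month or year, the end of follow-up or study exit, and death. Apply the follow-up or exit limit only where it falls within the recorded month or year, so that a known month is not overridden.
- Never impute an end earlier than the AE or medication start date. This clause alone would remove the inverted dates, but it would not correct on-treatment events that resolved in follow-up.

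In section 4.11.2, state that the AESI period of resolution is not derived from an imputed end date, and show such events as 'resolved, date incomplete'.

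As a wording clarification only, say in section 4.3.2.1 that 1 January is used for a completely missing start date only when the end date is before first dose.

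The cost is a few words and one change to the date derivation. The downside is that a few resolutions will appear later than they truly were, or with the period unknown.

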4.3.2.3 Imputation of Laboratory Values Outside of Quantification Range

Values of the form of “< x” (i.e., below the lower limit of quantification [LLOQ]) or > x (i.e. above the upper limit of quantification [ULOQ]) will be imputed as “x” in the calculation of summary statistics but displayed as “< x” or “> x” in the listings. Values of “≤ x” or “≥ x” will be imputed as well.

4.4 Software

All report outputs will be produced using SAS® version 9.4 or later in a secure and validated environment

4.5 Analysis Sets

The Enrolled Analysis Set will include all patients who sign the informed consent form.

The **Full Analysis Set (FAS)** is defined as all randomised patients, with treatment groups assigned in accordance with the randomisation, regardless of the actual treatment received. Patients who are randomised, but do not subsequently receive treatment will be included in the FAS. If a patient is allocated the incorrect study treatment as per the study randomisation list, patients will be summarised and analysed ‘as randomised’ i.e., by randomised treatment group.

There will be not statistical analyses of the FAS dataset as the primary endpoint analysis and summaries will be based on the PD analysis set.

PD analysis set.

A patient is considered to be evaluable for the PD analysis set if:

- the patient has taken a minimum of 5 consecutive daily doses of AZD9833 for Stage 1 and Stage 2; and the patient has taken a minimum of 12 consecutive daily doses of AZD9833 for Stage 3.
- the patient received the last dose of AZD9833 within 12 hours of on-treatment biopsy;
- the diagnostic and on-treatment biopsy pair are considered evaluable as below:
 - The diagnostic and on-treatment biopsy pair is considered evaluable by central pathology assessment, defined as containing > 100 tumour cells in each FFPE biopsy, and
 - A minimum of 2 slides to allow measurement of ER
- has no protocol deviations that may impact the biomarker analysis.

The PD analysis set will include all patients who have a pair of any of ER, PgR or Ki67 results and will show a missing category when no results are available for an individual biomarker. Note that, from Stage 1 and Stage 3, all evaluable patients were evaluable for all 3 markers. For all non-evaluable patients, all were non-evaluable for all 3 biomarkers, e.g. no tumour tissue.

For the PD analysis set, if a patient is allocated the incorrect study treatment as per the study randomisation list, patients will be summarised ‘as treated’, i.e., patients randomised to AZD9833 who received an incorrect AZD9833 dose at the randomisation visit, will be accounted for in the treatment group corresponding to the first AZD9833 dose they received.

The **Safety Analysis Set** is defined as all patients who received any amount of study treatment, regardless of whether that was the randomised therapy intended or whether they received therapy without being randomised. If a patient is allocated the incorrect study treatment as per the study

randomisation list, patients will be summarised ‘as treated’ i.e., patients randomised to AZD9833 who received an incorrect AZD9833 dose at the randomisation visit will be accounted for in the treatment group corresponding to the first AZD9833 dose they received. The safety summaries will be based on safety analysis set. Safety data will not be formally analysed.

PK summaries will be based on the **PK Analysis Set**. The PK Analysis Set is defined as all patients who received at least one dose of AZD9833 per protocol, for whom there is at least one reportable PK concentration. If a patient is allocated the incorrect study treatment as per the study randomisation list, patients will be summarised ‘as treated’ i.e., patients randomised to AZD9833 who received an incorrect AZD9833 dose at the randomisation visit, will be accounted for in the treatment group corresponding to the first AZD9833 dose they received.

Upon database release, protocol deviation and analysis set outputs will be produced and will be sent to AZ and the ICI for review. Prior to database lock, an analysis set classification meeting will be arranged, involving AZ and the ICI, to discuss the outputs and decide which patients and/or patient data will be excluded from certain analyses, these decisions will be documented. A similar review to determine PD analysis set classification will take place prior to the production of outputs for the SDMC and the Stage 2 interim analysis.

A summary on which analysis set will be used for each outcome variable is provided in [Table 3](#).

Table 3: Summary of Outcome Variables and Analysis Sets

Outcome Variable	Analysis Set
Study Population/Demography Data	
Disposition of patients	Enrolled
Demography characteristics	FAS*/Safety
Baseline and disease characteristics	FAS*/Safety
Important protocol deviations	FAS*/Safety
Medical/surgical history	FAS*/Safety
Previous anti-cancer therapy	FAS*/Safety
Concomitant medications/procedures	Safety
Subsequent anti-cancer therapy	Safety
PK Data	
PK concentrations	PK
Pharmacodynamic Data	
ER, PgR, Ki-67	PD Safety**
Safety Data	
Exposure	Safety
AEs	Safety
Laboratory measurements	Safety
Vital signs	Safety
ECGs	Safety

ER = oestrogen receptor; FAS = Full Analysis Set; PgR = progesterone receptor; PK = pharmacokinetic.

*Summary will be provided for safety analysis set; listings will be produced for the FAS analysis set.

**Pharmacodynamic data summaries will be based on PD analysis set, but listings will be provided for safety analysis set

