3.5 Planned Analysis

The study is open-label, and so all AstraZeneca (AZ) and Parexel (PXL) team members involved in this study will be unblinded throughout. The details of the analyses planned during the conduct of this study are outlined in [Table 1](#).

Table 1: Summary of Analyses during Study Conduct

Analysis	Trigger/Timepoint	Data included
End of Stage 1: Review by the SDMC	Upon completion of Stage 1 and availability of IHC data.	Data from Stage 1, including: Primary endpoint Key secondary endpoints Key safety data
Interim analysis Stage 2	Upon study completion of all patients recruited from Georgia and Mexico	Key data from Stage 1 and Stage 2, to include approximately 60 patients from Georgia and Mexico, and any available data from the UK patient population. Data to include: Primary endpoint Key secondary endpoints Key safety data
Final Stage 3 analysis ^a	Upon study completion of all patients recruited from Georgia and Mexico	Key data from Stage 3, to include approximately 48 patients from Georgia and Mexico, and any available data from the UK patient population. Data to include: Primary endpoint

		Key secondary endpoints Key safety data
Final analysis and CSR ^a	Following completion of the study and final database lock	All data from Stage 1, Stage 2 and Stage 3

^a In the event that UK stage 2 completes ahead of stage 3, a UK stage 2 specific interim analysis may be performed; Final stage 3 analysis and final analysis may be combined if appropriate

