4.6.2 Protocol Deviations

Important protocol deviations are defined as those deviations from the protocol likely to have a large impact on the interpretation of any analysis based on addressing the primary and secondary objectives of the trial.

The following general protocol deviation categories will be programmatically derived from the electronic case report form (eCRF) data. These deviations will be reviewed and assessed on a case-by-case basis by the study team to determine importance. Deviations considered to be important will be listed and discussed in the CSR as appropriate. All decisions on importance will be made ahead of database lock and will be documented prior to the analysis being conducted. Deviations will include, but are not limited to:

- Patients who deviate from inclusion /exclusion criteria per the Clinical Study Protocol (CSP) (Deviation 1).
- Patients who fail to sign the correct informed consent form, except the genetic informed consent form, before randomisation (Deviation 2).
- Patients whose baseline safety assessments as per CSP are missing (Deviation 3).
- Patients who received prohibited medications during the study (Deviation 4). Refer to the CSP Section 6.5 for those medications that are detailed as being ‘excluded’ from permitted use during the study. This will be used as a guiding principle for the physician review of all medications prior to database lock.
- Patients who don’t have a baseline biopsy (Deviation 5).
- Patients who don’t have an on-treatment biopsy (Deviation 6).
- Patients randomised who received an incorrect dose to that which they were randomised to (Deviation 7).
- Received AZD9833 and had an on-treatment biopsy more than 12 hours after last AZD9833 dose (Deviation 8).

- Pre- or on-treatment FFPE samples contain ≤ 100 tumour cells (Deviation 9).
- No on-treatment FFPE blocks provided (Deviation 10).
- Received AZD9833 and had an on-treatment biopsy without a minimum of 5 consecutive dosing days (Deviation 11).
- A minimum of 2 slides are not available from either the baseline or on-treatment biopsy (Deviation 12).

The following will be checked for analysis purposes and will not be included as part of the deviations to be recorded in the protocol deviations log during the study:

- Patients randomised but who did not receive any study treatment (Deviation 13).

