- Patient vomits on the day of PK sampling and within 8 hours of AZD9833 dosing (Deviation 14). These will be reviewed on a case-by-case basis to determine whether any exclusion from the PK analysis set is deemed necessary.
- Non-invasive tumour biopsy scorings (Deviation 15).

Patients who received the wrong treatment at any time will be included in the analysis set as described in [Section 4.5](#). During the study, decisions on how to handle errors in treatment dispensing (with regards to continuation/discontinuation of study treatment or, if applicable, analytically) will be made on an individual basis with written instruction from the study team leader and/or statistician.

Important protocol deviations will be listed and summarised by randomised treatment group. Important protocol deviations related to COVID-19 will be summarised separately.

Table 4: Summary of Deviations and Actions

Deviation	Action
Deviation 13	Exclusion from the Safety Analysis Set
Deviations 5, 6, 8-11 and 12	Patient becomes non-evaluable and to exclusion from the PD analysis set
Deviation 15	Exclusion of non-invasive tumour biopsy scorings from analysis
Other/further deviations	Will not lead to patients being excluded from the analysis sets described in Section 4.5 unless the deviation is considered to impact upon pharmacodynamic data. Non-evaluable patients will be replaced.

A per-protocol analysis excluding patients with specific important protocol deviations is not planned, however a sensitivity analysis may be performed on the key PD endpoints if $> 10\%$ of patients in any treatment group have any other significant deviation deemed to affect the primary endpoint which haven't already led to exclusion from the PD analysis set.

The need for such a sensitivity analysis will be determined following review of the protocol deviations ahead of database lock and will be documented prior to the analysis being conducted.

In addition to the programmatic determination of deviations above, other study deviations captured from the eCRF module for inclusion/exclusion criteria will be tabulated and listed. Any other deviations from monitoring notes or reports will be reported in an appendix to the CSR.

A full list of protocol deviations can be found in the study-specific Protocol Deviation Specification.

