4.14 SDMC Analysis and Reporting

Following the availability of the IHC data from the last evaluable patient in Stage 1, the SDMC will convene to review the Stage 1 data alone or potentially alongside emerging data from any relevant ongoing AZD9833 studies. The SDMC will make a decision on whether to proceed with Stage 2, based on the guidelines outlined in the SDMC charter and, if proceeding, will select up to four treatment groups for post-menopausal patients and confirm whether a pre-menopausal treatment group should be included. Refer to the SDMC charter and Section 9.6 of the CSP for more details on the SDMC members, SDMC recommendations and rationale for SDMC recommendations. Based on the data review, the recommendations of the SDMC may include but are not limited to:

- Continue the study to Stage 2 with a focus on lower AZD9833 doses.
- Continue the study to Stage 2 with a focus on higher AZD9833 doses.
- Increase the number of patients in Stage 2 at the same dose levels from Stage 1 to provide more precision.
- Add more dose levels of AZD9833.
- Add a fulvestrant group in stage 2.
- Add a pre-menopausal women AZD9833 treatment arm.

Analysis of tumour samples will be batched, and the resulting data reviewed on an ongoing basis throughout the study. Raw data will be plotted to provide information for the ongoing development of the clinical program.

Stage 1 data will be analysed and summarised following the methodology outlined in the previous sections of this SAP in an unblinded fashion. For the SDMC, only the Stage 1 data analysis and summaries will be provided by PXL.

The patient disposition, demographic characteristics, baseline patient and disease characteristics, study drug exposure, baseline and post-baseline safety parameters (AEs, clinical laboratory evaluations, vital signs, ECG data etc.) will be summarised. The primary/secondary endpoints will

be analysed as specified in [Section 4.10](#) of SAP. The list of tables, listings and figures required for the SDMC review will be prepared as described in the SDMC charter and as per AZ standards; and they will be flagged in the list of TLFs for the entire study.

Refer to [Section 1](#) for the SDMC recommendations for stage 2, and [Section 3](#) for the detailed investigational plan for stage 2.

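### Discretionary exclusions from the PD analysis set are not shielded from dose or biomarker values, and no planned analysis restores the patients removed

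*SAP*

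**What the plan says.** SAP section 4.5 bases the primary analysis on the PD analysis set and plans no statistical analysis of the FAS. PD-set membership rests on objective criteria: a minimum number of consecutive doses, biopsy within 12 hours of the last dose, more than 100 tumour cells in each biopsy, and at least 2 slides. One open criterion is added, that the patient "has no protocol deviations that may impact the biomarker analysis".

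Table 4 in section 4.6.2 follows the same pattern. For Deviations 5, 6 and 8 to 12 the action is fixed: "Patient becomes non-evaluable and to exclusion from the PD analysis set". Other deviations do not exclude a patient "unless the deviation is considered to impact upon pharmacodynamic data". Neither section lists which deviations would qualify. On the importance of deviations, section 4.6.2 says: "These deviations will be reviewed and assessed on a case-by-case basis by the study team to determine importance".

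Section 4.5 places the decision at a meeting of the sponsor (AZ) and the ICI before database lock, which is to "decide which patients and/or patient data will be excluded from certain analyses, these decisions will be documented". A similar PD classification precedes the SDMC outputs and the Stage 2 interim outputs.

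On access to information, section 3.5 states: "The study is open-label, and so all AstraZeneca (AZ) and Parexel (PXL) team members involved in this study will be unblinded throughout". Section 4.14 adds: "Analysis of tumour samples will be batched, and the resulting data reviewed on an ongoing basis throughout the study", and says that raw data will be plotted. Section 4.10 blinds the scoring pathologist to treatment group. No similar provision covers those who classify patients.

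**The concern.** When an exclusion depends on judgement, it should be made without knowledge of the result it affects. Here the judgement concerns whether a deviation matters for the biomarker, in an open-label study whose biomarker data are looked at continuously. If an unfavourable pair were dropped for a debatable deviation while a favourable pair with a similar deviation stayed in, the estimated ER reduction would be too large and its interval too narrow.

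Deciding before lock and documenting the decision makes the choice traceable. It does not make the choice independent of results that may already be visible. No planned analysis would reveal the effect either: the optional sensitivity analysis in section 4.6.2 concerns deviations that have not already led to exclusion, so it can only remove further patients.

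**Working it through.** **Where discretion remains.**

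| Step | What the SAP fixes | What it leaves open |
|---|---|---|
| Exclusion rule | Deviations 5, 6, 8 to 12 (Table 4) | Any other deviation judged to affect PD data (4.5, Table 4) |
| Who decides | AZ and the ICI (4.5) | Their access to IHC values; the ICI's knowledge of dose |
| Knowledge of dose | AZ and Parexel unblinded (3.5) | – |
| Sight of results | Ongoing review and raw plots (4.14) | Who carries these out |
| Blinding | Pathologist's scoring (4.10) | Classification of patients |
| Check on exclusions | PD listings for the safety set (Table 3 footnote) | Any model that restores excluded patients |

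**Reproducing the plan's precision figures.** Inputs from section 4.13: SD 29, two-sided 80% CI, 80% chance of meeting the half-width. The half-width met with 80% probability is

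t(0.90, n−1) × 29 × √[χ²(0.80, n−1)/(n−1)] / √n

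- n = 12: 1.363 × 29 × √(14.63/11) / √12 = 13.2 (stated: at most 14)
- n = 24: 1.319 × 29 × √(28.43/23) / √24 = 8.7 (stated: at most 9)
- n = 36: 1.306 × 29 × √(41.78/35) / √36 = 6.9 (stated: at most 7)

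The stated figures hold, so SD 29 is a fair basis for the illustration.

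**Worst-case effect of one exclusion.** Assumptions: normally distributed percent change, SD 29, simple group means, and the patient with the least reduction always being the one dropped. Removing the extreme value from n patients moves the mean by (extreme − mean)/(n−1), which in expectation is e(n) × 29/(n−1), where e(n) is the expected maximum of n standard normal values.

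- n = 12: 1.629 × 29/11 = 4.3 points, 31% of the stated 14
- n = 24: 1.948 × 29/23 = 2.5 points, 27% of the stated 9
- n = 36: 2.118 × 29/35 = 1.8 points, 25% of the stated 7

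A simulation of 100,000 samples per n gives the same shifts, and also the actual coverage of the nominal 80% interval:

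| n | Dropped | Mean shift (points) | Coverage of 80% CI |
|---|---|---|---|
| 12 | 1 | 4.3 | 71% |
| 12 | 2 | 8.0 | 57% |
| 24 | 1 | 2.5 | 74% |
| 24 | 2 | 4.5 | 63% |
| 36 | 1 | 1.8 | 75% |
| 36 | 2 | 3.3 | 67% |

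These are bounds for exclusion driven wholly by outcome. They do not estimate what happened in this trial.

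**The case against.** The case on the other side is substantial, and most of it stands.

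- **Most exclusions are not discretionary.** They follow numeric thresholds, and Table 4's default for every other deviation is to keep the patient. Only the residual clause is open.
- **The SAP suggests little use of that clause.** Section 4.5 records that non-evaluable patients were non-evaluable for all three markers and gives absence of tumour tissue as its example. Such a patient has no pair to select on. The accompanying sentence names Stages 1 and 3, so this is less informative for Stage 2.
- **Some transparency exists.** ER, PgR and Ki-67 listings cover the safety set, important deviations are listed, and PD classification also precedes the SDMC and interim outputs. A reader could trace an excluded pair by hand, although no model is planned for it.
- **The larger groups are less sensitive.** About 36 per group are expected at 75 mg and 150 mg when Stages 1 and 2 are pooled. In the final analyses a group of 12 applies only to 300 mg.

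A reader might go further and infer that the people at the meeting have already seen the biomarker results. That is plausible from sections 3.5 and 4.14 together, but section 4.14 does not say who reviews or plots the data, and the ICI's access is not described. A reader might also infer that exclusion costs nothing because non-evaluable patients are replaced. Replacement works only while recruitment is open; an exclusion at the final pre-lock meeting reduces n. Nor does the SAP show any scored pair being dropped because of its value.

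What survives is narrow: an open clause, no stated shielding of those who apply it, and no analysis that reverses it.

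**Conclusion.** The point holds as a gap in protection against bias, at low severity. For deviations outside the fixed rules, the SAP permits exclusion from the only set used for the primary endpoint, by judgement, without keeping dose or biomarker values from those who judge. In the worst case one exclusion uses roughly a quarter to a third of the stated half-width, and two in a group of 12 would bring an 80% interval down to about 57% coverage. These sizes assume normal data, SD 29, simple means rather than the planned ANCOVA, and exclusion driven entirely by outcome. Whether any discretionary exclusion was made cannot be told from the SAP. The aim is exploratory estimation with 80% intervals, so this is a cheap improvement and does not threaten the study's conclusions. No sample-size figure needs to change.

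**What to change.** Two changes to sections 4.5 and 4.6.2:

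1. For classifications still to be made, decide exclusions under the residual clause from a listing that omits dose and IHC values, and record the decisions before results are merged. The fixed-rule exclusions can stay as they are.
2. Add one sensitivity run of the ER ANCOVA that restores patients who have a scored pair and meet every objective PD-set criterion but were removed only under the discretionary clause. Do not widen it to every treated patient with a scorable pair. That would also bring back patients who fail the dosing or biopsy-timing criteria, and so answer a different question.

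The cost is one stripped listing, a slightly slower review and one model run. Masking comes too late for stages already classified, so for those the sensitivity run is the only protection. If there were no discretionary exclusions the run is empty, and saying so in the CSR would settle the matter.
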